Full study protocol and statistical analysis plan

Official Title of the study:

Analyses of Interleukin-6, Presepsin and Pentraxin-3 in the diagnosis and severity of late-onset preeclampsia

Date of the document:

October 2019.

Contents:

1. Participant Flow
2. Baseline Characteristics
3. Outcome Measures
4. Endpoints of the study
5. Limitations and Strengths
6. Certain Agreements
7. Results Point of Contact

1. Participant Flow

Recruitment Details

The study was conducted at Cengiz Gokcek Women's and Children's Hospital, Gaziantep, Turkey at department of obstetric and gynecology between date of June 2018 and January 2019. The study protocol was designed according to the Declaration of Helsinki, and the institutional ethical review board of Gaziantep University approved the study (Reference number: 2018/393). The investigators included subjects consisted of women with a singleton pregnancy who were diagnosed as having late-onset preeclampsia between 34+0 and 41+0 weeks of gestation. Pregnant women with uncomplicated pregnancies were randomly selected to serve as controls. The study was conducted with 44 late-onset preeclampsia patients as study group and 44 patients with normal pregnancies as control group. All participants included in the study gave oral and written informed consent.

Pre-assignment Details

The authors firstly were assessed the recruited people to ensure meeting the inclusion and exclusion criteria.

The inclusion criteria were made according to the official documents.

Arm/Group Information *

There are two groups in the study.

Arm/Group Title *

Preeclampsia group

Control group

2. Baseline Characteristics

The normal distribution of data is analysed with Kolmogorov Smirnov ve Shapiro Wilk tests. Student t test was used for variables that normally distributed for group comparison(L-PrE/kontrol) and Mann Whitney U test was used for variables that is not normally distributed. Also, Sperasman correlation was used for relationship of non-normally distributed variables with each other. The ROC analysis was applied for determination of cut-off points for IL6, presepsin ve pentraxin-3 variables. SPSS for Windows 22.0 ve Medcalc programs were used for statistical analysis. P<0.05 was accepted as statistical significance.

3. Outcome Measures

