Every participant in the study population underwent obstetric ultrasound examination and fetal-maternal assessment was carried out by one of the investigators. The obstetric anamnesis were obtained from all participants. The demographic data like age, gravidity, parity, body mass index (BMI) and gestational age were recorded. The gestational age was determined by calculation from the last menstrual period and supported by the ultrasonography measurements at first trimester of gestation. Maternal venous blood samples were taken for measurement of IL-6, presepsin and pentraxin-3 levels after the diagnosis of L-PrE in outpatient clinic. These samples quickly centrifuged at 1,500 g for 10 min, plasma samples were separated and stored at -80°C until the day of measurement. All patients with L-PrE were also hospitalized and their pregnancies were terminated. The samples of the control groups were obtained during the routine obstetrical care examination in the third trimester of pregnancy. Then these pregnant women were followed-up until the delivery. Both groups were compared in terms of maternal age, BMI, week of gestation, gravida, parity, live born, systolic/diastolic blood pressure, total protein in spot urine sample, hemoglobin, hematocrit, platelet count, white blood cell count, neutrophil, lymphocyte, neutrophil-to-lymphocyte ratio (NLR), urea, uric acid, albumin, blood urea nitrogen, creatinine, liver function tests (AST, ALT), lactic acid dehydrogenase, IL-6, presepsin, pentraxin-3, and infant weight at delivery. Neutrophil-to-lymphocyte ratio (NLR), which is the ratio of the neutrophils and lymphocytes in blood sample at admission, which can accept a marker of systemic inflammation. Small for gestational age (SGA) neonate was defined as birth weight <10th percentile for gestational age with Turkey's national nomogram as the reference for fetal growth. The maternal plasma presepsin levels were determined using a commercially available ELISA kit, the human presepsin ELISA Kit (Rel Assay Diagnostics, Gaziantep, Turkey), according to the manufacturer's instructions. Human presepsin ELISA kit is based on the principle of biotin double antibody sandwich technology. IL-6 levels in blood samples were measured by using the ELISA method (DIAsource ImmunoAssays SA, Nivelles, Belgium) in accordance with the method described by the manufacturer. Pentraxin-3 levels were measured by using the ELISA kits in accordance with the manufacturer's instructions (Sunredbio, Shanghai, PRC).

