
4. Endpoints of the study:

The primary endpoint in these analyses was IL-6, presepsin and pentraxin-3 levels in L-PrE group and control group.

The secondary endpoint was the IL-6, presepsin and pentraxin-3 levels in mild L-PrE group and severity L-PrE group.

Tertiary endpoint was the IL-6, presepsin and PTX-3 levels in SGA group and non-SGA group.

5. Limitations and strengths:

This study have some limitations. It was a small, observational and single-centered study. These three inflammatory markers were measured only during admission, we could not assess the changes in IL-6, presepsin, and pentraxin-3 in response to treatment due to lack of serial measurements.

We demonstrated, significant relations of all three elevated new inflammatory markers with both the presence and the severity of PrE at the same time in this study. Another strength of our study was that the women with PE had no pharmacological treatment. Because the antihypertensive drugs lead to the decrease in presepsin level due to the antiinflammatory effect.

6. Certain Agreements

The authors declare that they have no conflict of interest.

7. Results Point of Contact

Corresponding Author: [name], Cengiz Gokcek Public Hospital, Department of Obstetrics and Gynecology, Gaziantep/Turkey, [contact]

Address: [name]

GSM: [contact]

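### The primary marker comparison is not adjusted for recorded BMI, and no BMI matching of controls is described, so part of a modest marker difference could reflect BMI

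*Combined protocol and SAP*

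**What the plan says.** Section 1 (Participant Flow) describes the controls in one sentence: "Pregnant women with uncomplicated pregnancies were randomly selected to serve as controls". The group sizes follow: "The study was conducted with 44 late-onset preeclampsia patients as study group and 44 patients with normal pregnancies as control group". No matching variable is named. The section says that recruits were checked against inclusion and exclusion criteria, but does not list them.

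Section 3 (Outcome Measures) confirms that BMI is available: "The demographic data like age, gravidity, parity, body mass index (BMI) and gestational age were recorded". It does not say whether this is BMI before pregnancy, at booking or at sampling. BMI then appears once more, in the list of variables compared between the groups: "Both groups were compared in terms of maternal age, BMI, week of gestation, gravida, parity".

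The statistical methods are in section 2 (Baseline Characteristics). The parametric rule for comparing the groups reads "Student t test was used for variables that normally distributed for group comparison(L-PrE/kontrol". Its rank-based counterpart, equally without covariates, reads "Mann Whitney U test was used for variables that is not normally distributed". A Spearman "correlation was used for relationship of non-normally distributed variables with each other", ROC analysis sets a cut-off for each marker, and significance is P<0.05. No regression, analysis of covariance, stratification or covariate-adjusted ROC is described.

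Section 4 (Endpoints) states the target: "The primary endpoint in these analyses was IL-6, presepsin and pentraxin-3 levels in L-PrE group and control group". The limitations in section 5 are small size, observational design, a single centre and no serial measurements. Confounding is not mentioned.

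**The concern.** Random selection of controls is not random allocation. It makes the controls representative of uncomplicated pregnancies, but gives no reason to expect them to resemble the cases on BMI. Body size could plausibly be related both to preeclampsia and to circulating inflammatory markers. The documents give no evidence on either link, so this is a possibility to be checked and not a premise.

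The plan compares BMI between groups, but neither result of that comparison changes anything. A significant difference triggers no adjustment. A non-significant one is weak reassurance with 44 women per group. At stake is how the primary result is read: a crude marker difference may be taken as a relation with late-onset preeclampsia (L-PrE) itself when some of it belongs to BMI. The ROC separation could be inflated in the same way.

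Gestational age at sampling has the same gap, and here the documents show a reason for concern. Cases span 34+0 to 41+0 weeks (section 1), while controls were sampled at a routine third-trimester visit (section 3) with no narrower window described.

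**Working it through.** The plan states no effect size, SD, power or sample-size calculation, so it has no figure of its own to reproduce. The check asks how large a spurious result the unadjusted comparison could give.

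**Inputs from the documents.** n = 44 per group (section 1); significance at P<0.05 (section 2), taken as two-sided because the sidedness is not stated.

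**Assumed inputs.** BMI difference between groups, d = 0 to 0.8 SD; within-group correlation of BMI with the log marker, r = 0 to 0.4; no true L-PrE effect on the marker.

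**Step 1, spurious shift.** Shift in marker SD = d × r. Lower end: 0. Middle values: 0.6 × 0.3 = 0.18. Upper end: 0.8 × 0.4 = 0.32.

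**Step 2, false-positive rate.** The t statistic has noncentrality shift × √(44/2) on 86 degrees of freedom. For a shift of 0.32 this is 0.32 × 4.690 = 1.50. The spurious AUC is Φ(shift/√2).

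| d | r | Shift (SD) | P<0.05, one marker | Spurious AUC |
|---|---|---|---|---|
| 0, or r = 0 | any | 0 | 5.0% | 0.50 |
| 0.4 | 0.2 | 0.08 | 6.6% | 0.52 |
| 0.6 | 0.3 | 0.18 | 13.3% | 0.55 |
| 0.8 | 0.3 | 0.24 | 20.0% | 0.57 |
| 0.8 | 0.4 | 0.32 | 31.7% | 0.59 |

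**Step 3, simulation.** In 4,000 runs per scenario, at d = 0.8 and r = 0.4, the t test rejected in 31.8% and the Mann-Whitney test in 30.3%, so the choice between the two planned tests makes little difference. A linear model on group plus BMI rejected in 4.7%. Across all simulated scenarios that model stayed between 4.7% and 5.2%.

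**Step 4, what the planned BMI comparison can show.** Its power with 44 per group is about 29% at a difference of 0.3 SD, 46% at 0.4 SD, 64% at 0.5 SD and 96% at 0.8 SD. A large imbalance would probably be seen; a moderate one often would not.

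**Step 5, cost in precision.** Adding BMI multiplies the standard error of the group difference by about √[(1 − r²)(1 + d²/4)]. At d = 0.4, r = 0.4 this is √(0.84 × 1.04) = 0.93; at d = 0.8, r = 0.2 it is √(0.96 × 1.16) = 1.06. If either input may be zero, the range is √0.84 = 0.92 to √1.16 = 1.08. Adding gestational age changes this further, by an amount the documents do not allow one to compute.

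**The case against.** The strongest objection is that no bias is shown. It requires both a BMI difference and a BMI-marker correlation, and the documents report neither. With either at zero, the unadjusted tests keep their 5%. This stands, and it is why the range above starts at no bias. A reader might infer that the reported marker differences are a BMI effect; nothing in the documents supports that.

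A reader might also infer that the design does nothing to balance BMI. That too goes further than the text allows: the eligibility criteria are not listed, so a BMI restriction cannot be excluded. What can be said is that none is described. Drawing unmatched controls at random is itself a valid design, and matching is not being asked for.

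Third, the title's aim is diagnosis and severity. For a cut-off applied without regard to BMI, the crude ROC is a legitimate target. This stands, so the crude ROC should not be replaced. It does not answer the concern about the group comparison, where section 5 claims relations of all three markers with preeclampsia. A tempting rule would forbid any claim of a relation unless the BMI-adjusted difference excludes zero. That imposes a causal standard that the endpoint does not state, and a gate on BMI alone would ignore gestational age.

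Fourth, if BMI was measured after disease onset, it may partly reflect the disease, and adjustment could remove some of a real difference. This stands as a caution, and is a reason to show both results and to state when BMI was measured.

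Finally, the possible effect is modest, and a large marker difference would not be explained by it. Recruitment ended in January 2019 and results are already described, so the remedy is an added analysis rather than a change made in advance. Both points are correct; they limit the weight of the concern without removing it. Spearman correlations might have included BMI, but they would describe an association without taking it out of the group comparison.

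**Conclusion.** The point holds in conditional form. No BMI matching or restriction is described, BMI is recorded but only compared between groups, and the primary comparison stays unadjusted whatever that comparison shows. Part of a modest marker difference could therefore reflect BMI. Over the assumed ranges (d of 0 to 0.8 SD, r of 0 to 0.4, two-sided 5%, 44 per group, no true effect), the false-positive rate for one marker runs from 5% to about 32%, with a spurious AUC of at most about 0.59. These ranges are assumptions. The direction of any bias is assumed as well, and the same positive correlation need not apply to all three markers. The documents support a gap in the analysis; they do not support a finding that the results are biased. The gap merits correction because it touches the primary endpoint and can be closed with variables already recorded.

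**What to change.** Keep the t or Mann-Whitney tests and the crude ROC as stated. Beside them, for each of the three markers:

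- Fit a linear model of the log marker on group, recorded BMI as a continuous covariate, and gestational age at sampling. Report the adjusted group difference with its 95% interval.
- State when BMI was measured.
- Describe the marker's relation with L-PrE as independent of these covariates only where the adjusted interval excludes zero. Otherwise call it a crude association.

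Also state whether any eligibility criterion or matching rule concerned BMI.

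The cost is one extra model per marker, with no new data collection. For BMI alone, the standard error changes by about −8% to +8% over the assumed ranges. Intervals widen if the covariates differ strongly between groups. If BMI was measured after disease onset, the adjusted difference may be over-adjusted and should be read beside the crude one.

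### As a measure of fetal growth, the raw infant-weight comparison is confounded by gestational age at delivery; add a comparison standardised for gestational age.

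*Combined protocol and SAP*

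**What the plan says.** Section 3 (Outcome Measures) lists the variables on which L-PrE cases and controls are compared. The last is "infant weight at delivery". Week of gestation is a separate item, without saying whether it refers to sampling or to delivery.

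The tests are in Section 2 (Baseline Characteristics): a Student t test where a variable is judged normal and a Mann-Whitney test otherwise. The threshold is given as "P<0.05 was accepted as statistical significance". No covariate model is described.

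The groups reach delivery by different routes:

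- **Cases.** Section 1 enrols women "diagnosed as having late-onset preeclampsia between 34+0 and 41+0 weeks of gestation". Section 3 adds: "All patients with L-PrE were also hospitalized and their pregnancies were terminated". The interval from diagnosis to delivery is not given.
- **Controls.** Section 1 selects them at random from uncomplicated pregnancies and mentions no matching. Section 3 has them sampled at a routine third-trimester visit and adds: "Then these pregnant women were followed-up until the delivery".

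Section 3 does allow for gestational age in one place. It defines a small-for-gestational-age (SGA) neonate as "birth weight <10th percentile for gestational age", using a national nomogram. Section 4 uses SGA status only to group the marker levels for the tertiary endpoint. SGA is not in the list of L-PrE/control comparisons.

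**The concern.** Birth weight rises with gestational age, and here the way a pregnancy ends is tied to the group. If cases deliver earlier on average, their infants weigh less even when growth at each week is the same in both groups. An unadjusted test cannot separate that from slower growth.

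The plan recognises the dependence when it defines SGA, yet leaves the case-control weight comparison raw. As listed, no L-PrE/control comparison of infant size allows for gestational age. The stake is one of interpretation: a significant weight difference, reported in a study that also analyses SGA, could be taken as evidence of growth restriction when some or all of it reflects earlier delivery.

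**Working it through.** The document gives no birth-weight SD, delivery week or power figure, so there is no stated number to reproduce. The check asks how often the raw test would reach p<0.05 if growth were identical and only delivery timing differed.

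**Inputs from the document**
- Group sizes (Section 1): "The study was conducted with 44 late-onset preeclampsia patients as study group and 44 patients with normal pregnancies as control group", so n = 44 per group.
- Significance level 0.05 (Section 2). Sidedness is not stated; two-sided is assumed.

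**Assumptions, none of them in the document**
- Gap in mean gestational age at delivery, w: 0 to 3 weeks.
- Weight gain, g: 100 to 250 g per week, with 200 as the central value.
- SD of birth weight: 400 to 600 g, with 500 as the central value.

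**Step 1: yardstick.** The standard error of the difference is SD × √(2/44) = 0.2132 × SD, or 106.6 g at SD 500 g. A difference is just significant at 1.960 × 0.2132 = 0.418 SD (209 g). It is detected with 80% probability at (1.960 + 0.842) × 0.2132 = 0.597 SD, which is about 239, 299 and 358 g for SDs of 400, 500 and 600 g.

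**Step 2: rejection rate from timing alone.** The difference is w × g. The rate is Φ(wg/SE − 1.960) + Φ(−wg/SE − 1.960), a normal approximation. For w = 1 at the central values, wg/SE = 200/106.6 = 1.876, and Φ(−0.084) plus a negligible second term gives 46.7%.

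| Gap (weeks) | Difference at 200 g/week | Rate, SD 500 g | Range over all assumed g and SD |
|---|---|---|---|
| 0 | 0 g | 5% | 5% |
| 0.5 | 100 g | 15.5% | 7% to 31% |
| 1 | 200 g | 46.7% | 12% to 83% |
| 2 | 400 g | 96.3% | 35% to over 99% |
| 3 | 600 g | over 99.9% | 65% to over 99% |

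The exact noncentral t calculation at SD 500 g gives nearly the same: 45.8% at 200 g and 96.0% at 400 g. The gap needed for an 80% rejection rate runs from 0.96 weeks (SD 400 g, 250 g/week) to 3.58 weeks (SD 600 g, 100 g/week).

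**Step 3: timing share when growth also differs.** With a true growth deficit d, timing accounts for wg/(wg + d) of the raw difference. For gaps of 0.5, 1, 2 and 3 weeks:
- g = 200 g/week, d = 200 g: 33%, 50%, 67%, 75%.
- g = 100 g/week, d = 400 g: 11%, 20%, 33%, 43%.

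The deficits are also assumptions. Timing can be the smaller or the larger part.

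**Step 4: after standardisation.** If weight is compared at equal gestational age and the adjustment is correctly specified, the timing part drops out. The rejection rate with no growth difference then returns to 5%.

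**The case against.** The strongest reply is that the plan never says this row measures fetal growth. As a description of how infant weight differed between the groups, the raw comparison is valid whatever the cause. If earlier delivery follows from the disease, gestational age at delivery lies on the path from disease to weight, and conditioning on it answers a different question. This stands as a reason to keep the raw figure. It is no argument against adding a standardised comparison, which is the one needed to judge growth.

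Second, infant weight is not a primary, secondary or tertiary endpoint; all three are marker levels (Section 4). That stands, and it limits the importance of the point. A reader might infer that the SGA analysis is compromised too. It is not: SGA is already defined relative to gestational age, and the raw case-control weight difference does not enter it.

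Third, week of gestation is compared in the same list. If it means week at delivery, readers would see any timing gap beside the weight. The document does not say so, and a separate test of gestational age would not adjust the weight comparison.

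Fourth, a reader might infer that the raw test mostly measures timing, or will very probably be significant without any growth difference. The document does not support either. It gives no delivery weeks and no interval from diagnosis to delivery, and diagnosis may be as late as 41+0 weeks, so the gap could be small. Even within the assumptions used here, the rejection rate at one week ranges from 12% to 83%.

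**Conclusion.** The point holds as a minor one. Used to judge fetal growth, the L-PrE/control comparison of raw infant weight is confounded by gestational age at delivery: the groups come to delivery by different routes, and neither matching nor adjustment is described.

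Its size cannot be established from the document. The figure of about 15% to over 99% false significance for gaps of 0.5 to 3 weeks rests entirely on the assumed gap, 200 g per week and SD 500 g. With no gap the rate is the nominal 5%. Nothing here shows that an observed difference would be due to timing rather than to true growth restriction. The primary, secondary and tertiary marker endpoints are unaffected.

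**What to change.** 1. Report gestational age at delivery by group, and state whether the listed week of gestation is at sampling or at delivery.
2. Keep raw infant weight as a descriptive row.
3. Base any between-group inference about infant size on birth-weight percentile or z-score for gestational age from the national nomogram already cited. If only the 10th-percentile cut-off is available, compare SGA rates instead. A linear model for weight with group and gestational age at delivery as terms is an alternative.

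**Cost.** A sentence or two of text and a little extra analysis. Birth weight and gestational age at delivery are what SGA classification already requires. The document does not say that the nomogram was applied to controls, so it would have to be applied to both groups. The standardised result describes size at equal gestational age, not the total weight difference, and should be labelled that way.

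### The mild versus severe marker comparison has no adjustment for gestational age at sampling, so a difference in timing may be mixed with severity

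*Combined protocol and SAP*

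**What the plan says.** The severity question is set out in section 4 (Endpoints of the study): "The secondary endpoint was the IL-6, presepsin and pentraxin-3 levels in mild L-PrE group and severity L-PrE group". No covariate and no test is named there.

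The analysis methods are in section 2 (Baseline Characteristics). The parametric group comparison reads: "Student t test was used for variables that normally distributed for group comparison(L-PrE/kontrol". The rank-based alternative carries no covariate either and does not mention severity groups. Spearman correlation and ROC cut-offs complete the list after the normality tests. Regression, analysis of covariance, matching and stratification appear nowhere.

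On timing, section 1 (Participant Flow) describes cases as "diagnosed as having late-onset preeclampsia between 34+0 and 41+0 weeks of gestation". Section 3 (Outcome Measures) says: "Maternal venous blood samples were taken for measurement of IL-6, presepsin and pentraxin-3 levels after the diagnosis of L-PrE in outpatient clinic". Section 5 (Limitations and strengths) adds: "These three inflammatory markers were measured only during admission", with no serial measurements.

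On the covariate, section 3 says: "The demographic data like age, gravidity, parity, body mass index (BMI) and gestational age were recorded". It dates pregnancies from the last menstrual period with first-trimester ultrasound support. Section 3 also lists week of gestation among the variables compared between the two groups, which section 1 defines as preeclampsia and control. No such comparison is stated for mild versus severe.

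Section 5 already reports that all three markers are significantly related to severity as well as to presence of disease.

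**The concern.** A shared eligibility window limits gestational age but does not balance it within the window. Each woman gives one blood sample after diagnosis, so the week of sampling follows the week of diagnosis. If mild and severe disease tend to be diagnosed at different weeks, the two groups are also sampled at different weeks. If a marker changes with gestational age, an unadjusted difference then contains a timing component. This can add to a severity effect, stand in for one that does not exist, or cancel part of a real one.

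At stake is the severity half of the study's message, which is in the title and claimed as a finding in section 5. A reader cannot check the point from what is planned: gestational age is not tabulated by severity, and the limitations do not mention sampling time.

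**Working it through.** The documents contain no sample-size calculation, effect size or SD, so there is no design figure to reproduce.

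**Inputs from the documents**
- Cases: 44 (section 1). The numbers of mild and severe cases are not given.
- Eligibility window: 41+0 minus 34+0 = 7 weeks (section 1).
- Significance level: 0.05 (section 2). Sidedness is not stated; two-sided is assumed.

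**Assumed inputs**
- Split of the 44 cases: 22/22, 29/15 or 34/10.
- Correlation r between marker and gestational age within a severity group: 0 to 0.5.
- Gap g between the severity groups in mean gestational age at sampling: 0 to 1.0 SD. If presentation were uniform over the window, the SD would be 7/√12 = 2.02 weeks, so 0.5 to 1.0 SD is about 1 to 2 weeks. The observed spread is not reported.

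**Step 1: spurious difference.** With no true severity effect, the expected difference in marker SD units is r × g. Over the non-zero assumptions it runs from 0.2 × 0.5 = 0.10 to 0.5 × 1.0 = 0.50.

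**Step 2: false-positive rate of the unadjusted t test.** The noncentrality is (r × g)/√(1/n1 + 1/n2), with 42 degrees of freedom and critical value 2.018. At 22/22, r = 0.3 and g = 1.0, it is 0.30/√(2/22) = 0.995, which gives a rejection rate of 16.3%.

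| Split | r or g = 0 | r = 0.2, g = 0.5 | r = 0.3, g = 1.0 | r = 0.5, g = 1.0 |
|---|---|---|---|---|
| 22/22 | 5.0% | 6.2% | 16.3% | 36.7% |
| 29/15 | 5.0% | 6.1% | 15.2% | 33.6% |
| 34/10 | 5.0% | 5.8% | 12.9% | 27.4% |

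**Step 3: cross-check by simulation.** The simulation had no true severity effect, a gestational-age SD of 1.8 weeks, gaps of 1 or 2 weeks (0.56 or 1.11 SD), r from 0.2 to 0.5, and splits of 22/22 and 29/15. The t test rejected in 6.5% to 43.7% of runs. The top end is higher than in the table because the largest gap is wider. Mann-Whitney behaved similarly, up to about 41%. A linear model with gestational age as covariate rejected in 4.6% to 5.3% of runs in every scenario, including those with r or the gap at zero.

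**Step 4: what adjustment does to precision.** The covariate removes a fraction r² of the residual variance. When gestational age differs between equal groups, collinearity multiplies the variance of the severity estimate by about 1 + g²/4. The net ratio to the unadjusted variance is (1 − r²)(1 + g²/4):
- r = 0.2, g = 0.5: 0.96 × 1.0625 = 1.02
- r = 0.2, g = 1.0: 0.96 × 1.25 = 1.20
- r = 0.3, g = 0.5: 0.91 × 1.0625 = 0.97
- r = 0.3, g = 1.0: 0.91 × 1.25 = 1.14
- r = 0.5, g = 1.0: 0.75 × 1.25 = 0.94

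Precision may therefore improve slightly or worsen. It is not a reason to adjust.

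**The case against.** **The harm is conditional.** The documents give no correlation, no gap and no split, and 7 weeks is the eligibility range, not the observed spread. If the markers do not vary with gestational age, or if mild and severe cases were sampled at similar weeks, the unadjusted test keeps its 5% level. At the low end of the assumptions the rate is only about 6%. This stands. A reader might infer that the reported severity relation is a product of timing, or that its p-values are invalid. The documents support neither; they show only that the possibility was left unchecked.

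**The mild versus severe test is itself unspecified.** The t-test sentence names only L-PrE versus control, and mild and severe are not defined. This also stands. That the comparison is unadjusted is read from the absence of any adjusting method in the plan. Spearman correlation could describe how a marker relates to gestational age, but it does not adjust the group comparison.

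**Gestational age at diagnosis may partly reflect severity.** If more severe disease presents at a different week for that reason, conditioning on gestational age changes the question. In addition, recruitment ended in January 2019, and the document, dated October 2019, already states results. Both facts count against making an adjusted model the main result in place of the stated comparison. They do not count against showing it alongside.

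**Section 5 concedes a small, observational, single-centre study.** That is true, but it does not mention differences in sampling time.

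**Conclusion.** The point holds as a possible bias, not a demonstrated one. The plan compares markers between mild and severe L-PrE without accounting for gestational age at sampling. The design does nothing to equalise that variable between the two groups, and no check of its balance is stated, although the variable is recorded.

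Under the stated assumptions at 22/22, the false-positive rate per marker is about 6% to 37% instead of 5%, and 5% if the correlation or the gap is zero. With opposite signs the same mechanism could hide a real difference. The direction and size in this study cannot be judged until gestational age is reported by severity. The severity claim in section 5 should therefore be treated as unadjusted. It is a secondary endpoint and the check is cheap, so the sponsor should do it.

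**What to change.** 1. Report the numbers of mild and severe cases, and gestational age at sampling in each group (mean and SD, or median and quartiles).
2. Within the 44 L-PrE cases, fit a model of each marker on severity (mild or severe) plus gestational age at sampling as a continuous covariate. Log-transform the marker if it is skewed, or use rank ANCOVA.
3. Present the adjusted estimate with its 95% CI beside the unadjusted test, labelled post hoc. State that gestational age at diagnosis may itself partly reflect severity. With rank ANCOVA, the estimate and CI are on the rank scale and should be described that way.
4. If the severity relation does not survive adjustment for a marker, soften the statement in section 5 for that marker. Otherwise, say that it was checked.

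The cost is one regression per marker (three in all) on data already held and one degree of freedom (42 to 41), with no new patients or assays. Precision may also fall: the variance is about 1.14 times the unadjusted one at r = 0.3 and a 1 SD gap. That is the price of reducing a possible bias.
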